#### **Cockcroft-Gault**

$\text{GFR [mL/min]} = [(140 - \text{A}) \times \text{weight} / (72 \times \text{C})] \times (0.85 \text{ if female})$ , where  
C is the serum concentration of creatinine [mg/dL] and A is age (years).

#### **MDRD-4 formula**

$\text{eGFR [mL/min/1.73m}^2\text{]} = \text{eGFR} = 186.3 \times \text{C}^{-1.154} \times \text{A}^{-0.203} \times \text{G} \times \text{R}$ , where  
C is the serum concentration of creatinine [mg/dL],  
A is age (years), G=0.742 when gender is female, otherwise G=1,  
R=1.21 when race is black, otherwise R=1.

**Graft function:**

The incidence of acute rejection episodes, of CMV and HCV infections will be assessed.

**• Acute rejection episodes**

Acute rejection is defined as a clinically suspected acute rejection, whether biopsy-proven or not, which has been treated and confirmed by the investigator according to the response to therapy. Each acute rejection must be recorded on the relevant CRF page with the clinical diagnosis specified, and, if a biopsy was performed, with the histological diagnosis.

**• Biopsy-proven acute rejection**

Biopsy-proven acute rejection (BPAR) is defined as a clinically suspected acute rejection confirmed by biopsy. For all clinically suspected rejection episodes a graft biopsy is performed at investigator's discretion before or within a 24-hour period from the initiation of anti-rejection therapy. The local pathologist will grade biopsies. The results of the biopsy read by the local pathologist will be listed in the Allograft Biopsy CRF page.

**• Graft loss**

The allograft will be presumed to be lost if a patient has a liver retransplant or dies due to liver failure.

The reason for graft loss will be recorded on the Graft Loss CRF page. If graft loss occurs after the patient has discontinued study medication prematurely, the graft loss will be entered on the Study Completion and Graft Loss CRF page. Graft loss is considered a Serious Adverse Event and must be reported.

**• Death**

In the event of patient death, a SAE form including the event leading to death must be completed and faxed to Novartis CS&E within 24 hours. The events leading to the death must be entered on the AE CRF page and the death must be indicated on the Premature Discontinuation and on the Study Completion CRF pages.

**• HCV infection**

The evolution of Hepatitis C (HCV) and the rate of progression of HCV related allograft fibrosis will be evaluated. The HCV viral load, the incidence of and response to HCV antiviral treatment and the incidence of de novo hepatocellular carcinoma (HCC) malignancies and the rate of recurrence of HCC will be assessed. Biopsies will be obtained in all patients who are listed as HCV positive by serology testing, at time of transplantation and at Month 12. The biopsies will be read by the local pathologist (who will remain blinded to patient treatment) according to the Ishak-Knodell scores (Ishak 1995) (see Appendix 9).

## 7.6 Safety

### 7.6.1 Adverse events

An adverse event is the appearance or worsening of any undesirable sign, symptom, or medical condition occurring after start of study drug even if the event is not considered to be related to study drug. Medical conditions/diseases present before obtaining informed consent have to be documented as medical history and are only considered adverse events if they worsen after study start. Abnormal laboratory values or test results constitute adverse events only if they induce clinical signs or symptoms, require study drug discontinuation or require therapy.

The occurrence of adverse events should be sought by non-directive questioning of the patient at each visit during the study. Adverse events also may be detected when they are volunteered by the patient during or between visits or through physical examination, laboratory test, or other assessments. All adverse events must be recorded on the Adverse Events CRF with the following information:

1. the severity grade (mild, moderate, severe)
2. its relationship to the study drug (everolimus) and tacrolimus (suspected/not suspected)
3. its duration (start and end dates or if continuing at final exam)
4. whether it constitutes a serious adverse event (SAE)

An SAE is defined as an event which:

- is fatal or life-threatening
- results in persistent or significant disability/incapacity
- constitutes a congenital anomaly/birth defect
- requires inpatient hospitalization or prolongation of existing hospitalization, unless hospitalization is for:
  - routine treatment or monitoring of the studied indication, not associated with any deterioration in condition
  - elective or pre-planned treatment for a pre-existing condition that is unrelated to the indication under study and has not worsened since the start of study drug
  - treatment on an emergency outpatient basis for an event not fulfilling any of the definitions of a SAE given above and not resulting in hospital admission
  - social reasons and respite care in the absence of any deterioration in the patient's general condition
  - treatment of acute rejection; acute rejections are considered to be a protocol exempted event. They should not be reported simply because they result in a hospitalization and thus meet the criteria for an SAE. Acute rejections should be reported as SAEs only if they are unusual in appearance, clinical course and/or are graft threatening
- is medically significant, i.e., defined as an event that jeopardizes the patient or may require medical or surgical intervention to prevent one of the outcomes listed above
- is a graft loss

**Unlike routine safety assessments, SAEs are monitored continuously and have special reporting requirements; see [Section 8.1](#).**

All adverse events should be treated appropriately. Treatment may include one or more of the following: no action taken (i.e., further observation only); study drug dosage adjusted/temporarily interrupted; study drug permanently discontinued due to this adverse event; concomitant medication given; non-drug therapy given; patient hospitalized/patient's hospitalization prolonged, Other immunosuppressant taken/adjusted, concomitant medication stopped. The action taken to treat the adverse event should be recorded on the Adverse Event CRF.

Once an adverse event is detected, it should be followed until its resolution or until it is judged to be permanent, and assessment should be made at each visit (or more frequently, if necessary) of any changes in severity, the suspected relationship to the study drug, the interventions required to treat it, and the outcome.

Information about common side effects already known about the investigational drug can be found in the Investigator Brochure or will be communicated between IB updates in the form of Investigator Notifications. This information will be included in the patient informed consent and should be discussed with the patient during the informed consent process and the study as needed.

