## Glossary of terms

Assessment	A procedure used to generate data required by the study
Control drug	A study drug used as a comparator to reduce assessment bias, preserve blinding of investigational drug, assess internal study validity, and/or evaluate comparative effects of the investigational drug
Enrollment	Point/time of patient entry into the study; the point at which informed consent must be obtained (i.e., prior to starting any of the procedures described in the protocol)
Investigational drug	The study drug whose properties are being tested in the study
Patient number	A number assigned to each patient who enrolls in the study; when combined with the center number, a unique identifier for each patient in the study is created.
Phase	A major subdivision of the study timeline; begins and ends with major study milestones such as enrollment, randomization, completion of treatment, etc.
Period	A minor subdivision of the study timeline; divides phases into smaller functional segments such as screening, baseline, titration, washout, etc.
Premature patient withdrawal	Point/time when the patient exits from the study prior to the planned completion of all study drug administration and assessments; at this time all study drug administration is discontinued and no further assessments are planned
Randomization number	A unique identifier assigned to each randomized patient, corresponding to a specific treatment arm assignment
Study drug	Any drug administered to the patient as part of the required study procedures; includes investigational drug and any control drugs
Study drug discontinuation	Point/time when patient permanently stops taking study drug for any reason; may or may not also be the point/time of premature patient withdrawal
Variable	Information used in the data analysis; derived directly or indirectly from data collected using specified assessments at specified timepoints

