### 13.5 Appendix 5: Guidelines for everolimus dose reduction

An investigator may interrupt temporarily or reduce the dosage of everolimus, if in his/her opinion this is clinically warranted, in response to any causally associated AE (e.g., neutropenia, thrombocytopenia, leukocytopenia, hyperlipidemia, hypertriglyceridemia). The following guidelines should be followed:

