#### 1- PLATELETS

Platelet count < 75,000/mm^3

Step 1: dose reduction should be considered and the first dose reduction may be instituted at the discretion of the Investigator.

Step 2: if the platelet count remains below 75,000/mm^3 despite the initial dose reduction, a further dose reduction may be implemented per the table below.

Platelet count < 50,000/mm^3 Dose interruption should be considered.

Platelet count < 30,000/mm^3 Dose interruption will be mandatory.

If the platelet count returns to 50,000/mm^3 for 3 days, everolimus may be restarted at lowest reduced dose. If the platelet count is stable at the reduced dose for 3 days, everolimus may be increased to the next higher dose. If the platelet count remains stable at greater than 75,000/mm^3 for 7 days, the full dose of everolimus may be restarted.

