#### 2- HEMOGLOBIN

Hemoglobin < 8 g/dL

Step 1: dose reduction should be considered and the first dose reduction may be instituted at the discretion of the Investigator.

Step 2: if the hemoglobin remains below 8 g/dL despite the initial dose reduction, a further dose reduction may be implemented per the table below.

Hemoglobin < 6 mg/dL: dose interruption will be mandatory.

Once hemoglobin returns to > 6 mg/dL for 3 days, everolimus may be restarted at the lowest (one

tablet b.i.d) level. If the hemoglobin is stable at the reduced dose for 3 days, everolimus may be increased to the next higher dose. Once hemoglobin returns to levels > 8 mg/dL for 7 days, everolimus may be increased to the full dose.

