#### **4- CHOLESTEROL**

Cholesterol > 300 mg/dL or > 8 mmol/L:

Dietary instruction is strongly recommended and statin therapy, e.g. fluvastatin, should be considered.

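### The laboratory rule in Protocol 7.6.1 does not name dose reduction or temporary interruption, while Appendix 5 manages cytopenias that way and calls them adverse events

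*Protocol*

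**What the plan says.** - **AE definition (Protocol 7.6.1).** "Abnormal laboratory values or test results constitute adverse events only if they induce clinical signs or symptoms, require study drug discontinuation or require therapy". Dose reduction and temporary interruption are not in that list.
- **Meaning of discontinuation (Protocol glossary).** "Point/time when patient permanently stops taking study drug for any reason".
- **Appendix 5, opening.** The investigator may interrupt or reduce everolimus "in response to any causally associated AE (e.g., neutropenia, thrombocytopenia, leukocytopenia, hyperlipidemia, hypertriglyceridemia".
- **Appendix 5, blood counts.** Below the first platelet threshold, "dose reduction should be considered and the first dose reduction may be instituted at the discretion of the Investigator". Below 30,000/mm³, "Dose interruption will be mandatory". Hemoglobin follows the same ladder: "if the hemoglobin remains below 8 g/dL despite the initial dose reduction, a further dose reduction may be implemented per the table below". White cells follow it too. None of the three ladders names any measure other than changing the everolimus dose.
- **Protocol 6.6.3, everolimus.** Severe leukocytopenia and thrombocytopenia are described as hematologic adverse events for which everolimus is interrupted.
- **Protocol 7.6.1, later paragraph.** The list of what treatment of an AE may include has the entry "study drug dosage adjusted/temporarily interrupted".
- **Other safety outputs.** Protocol 10.3.1 and SAP 2.3.1 tabulate dose reductions, including interruptions, by reason and arm. Protocol 10.5.2 and SAP 2.6.3 summarize notable values against Appendix 2 and describe every laboratory variable by visit and arm.

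**The concern.** The section that decides what goes on the AE form is restrictive, and the sections that tell the investigator how to handle cytopenias assume that these are already AEs. An investigator who follows 7.6.1 to the letter has no reason to open an AE record for a low count that is managed only by changing the everolimus dose. One who follows 6.6.3 or Appendix 5 does.

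Without an AE record the event has no severity grade, no relationship assessment and no seriousness assessment, and it is missing from every AE table. The trial is open-label, runs at 15 centers and uses local laboratories, so recording habits can differ between sites. The protocol and SAP also list as a safety objective the incidence and reason, with AE as the example, for interruption and dose adjustment. That objective works best when dose changes and AE records match.

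**Working it through.** The plan states no figure on this point. The check sets the passages side by side.

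**Step 1. Apply the rule to a case.** Take platelets of 25,000/mm³ with no bleeding and no transfusion.

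- Signs or symptoms: none.
- Study drug discontinuation: no. Appendix 5 requires an interruption with a path to restart, and the glossary reserves discontinuation for a permanent stop.
- Therapy: none given beyond withholding everolimus.

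Read literally, 7.6.1 does not make this an AE. Section 6.6.3 and the opening of Appendix 5 both call it one. The same conflict arises for hemoglobin and white cells. A transfused anemia is outside it, because transfusion is therapy.

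**Step 2. See whether the notable-value tables pick these events up.** Compare the Appendix 5 action thresholds with the Appendix 2 notable criteria.

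| Variable | Appendix 5: reduction considered | Appendix 5: interruption mandatory | Appendix 2: notable low | Reduction range that is not notable |
|---|---|---|---|---|
| Platelets (/mm³) | <75,000 | <30,000 | <50,000 | 50,000 to <75,000 |
| Hemoglobin (g/dL) | <8 | <6 | <7 | 7 to <8 |
| White cells (/mm³) | <3,000 | <1,500 | ≤2,000 | >2,000 to <3,000 |

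For hemoglobin, the Appendix 5 text prints some limits in mg/dL; its table heading and Appendix 2 use g/dL, which I have assumed throughout.

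Every mandatory-interruption value is notable (30,000 < 50,000; 6 < 7; 1,500 < 2,000). Such an event appears in the laboratory tables even with no AE record. In the last column it is neither a notable value nor, read literally, an AE.

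**Step 3. See what remains for the last column.** Two outputs remain: dose reductions by reason (SAP 2.3.1) and descriptive statistics by visit (SAP 2.6.3). Neither carries severity, causality or seriousness. Protocol 10.5.2 also planned a graphical display of shifts to the worst post-baseline value; SAP 2.6.3 does not carry it, and SAP section 4 does not list its removal. The AE summaries in SAP 2.6.1 single out events leading to permanent discontinuation, not those leading to reduction or interruption.

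**Step 4. Check lipids separately.** For cholesterol the first step in Appendix 5 is "Dietary instruction is strongly recommended and statin therapy, e.g. fluvastatin, should be considered". Triglycerides are handled alike, and everolimus is changed only if the abnormality persists. Section 6.6.6 puts optimizing lipid-lowering medication ahead of any dose reduction. An elevation that reaches the dose-change step will therefore normally have met the therapy limb of 7.6.1. The exception is a case managed by diet and dose change alone, with no lipid-lowering drug. Even that is arguable, since 7.6.1 lists non-drug therapy among treatments.

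**The case against.** **A dose change may itself count as therapy.** The later paragraph of 7.6.1 lists dose adjustment and interruption among the forms that treatment of an AE can take, so the therapy limb could be read to include them. This makes the wording less clear but does not resolve it. The same list contains taking no action, so importing it into the rule would turn every abnormal value into an AE. It also contains permanent discontinuation, which would make the separate discontinuation limb pointless. The paragraph governs events that already qualify as AEs.

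**The protocol elsewhere plainly treats these findings as AEs.** Section 6.6.3 ties everolimus reduction and interruption for intolerance to the occurrence of adverse events. That stands, and it is why the defect is a conflict between sections and not a settled rule of exclusion. Many investigators may have recorded these events as AEs.

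**The information is not lost.** This stands in large part. All dose changes and their reasons go on the Dosage Administration Record, dose reductions by reason are tabulated by arm, and laboratory values are summarized separately. A reader might infer that these events cannot be linked to the reason for a dose change; the documents do not support that. What is missing is the AE record and its assessments.

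**The clause is not specific to everolimus.** This also stands. Section 6.6.3 provides for tacrolimus reduction in severe toxicity in either arm, and its acute kidney injury rule lowers tacrolimus as well as everolimus. An asymptomatic laboratory abnormality managed by lowering tacrolimus falls under the same wording.

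**Conclusion.** The point holds as an inconsistency that should be corrected. Section 7.6.1, taken literally with the glossary, leaves out asymptomatic low platelets, hemoglobin or white cells that are managed only by dose reduction or temporary interruption, while section 6.6.3 and Appendix 5 call such findings adverse events. The consequence is confined to the AE tables and the assessments attached to AE records. It is greatest in the three ranges that also escape the notable criteria: platelets 50,000 to <75,000/mm³, hemoglobin 7 to <8 g/dL and white cells >2,000 to <3,000/mm³.

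Two stronger readings are tempting and are not supported. One is that the AE comparison is biased in favor of everolimus. Appendix 5 covers everolimus only, so that direction is plausible, but the clause applies equally to tacrolimus dose changes in both arms, and the documents give no frequencies from which a net direction or size could be derived. The other is that lipid elevations are affected in the same way; mostly they are not, because lipid-lowering therapy comes first.

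The conclusion assumes that some sites apply 7.6.1 as written. How many do so cannot be determined from the documents.

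**What to change.** **Protocol wording.** Reconcile 7.6.1 (both paragraphs), 6.6.3 and Appendix 5 on what is recorded as an AE. The simplest way is to add to the laboratory clause of 7.6.1 abnormalities that lead to dose reduction or temporary interruption of study drug because of toxicity. Exclude dose changes made only to keep everolimus or tacrolimus trough levels in the target range; otherwise routine drug monitoring in both arms would generate AEs. Name both drugs, because 7.6.1 puts everolimus in brackets after study drug and lists tacrolimus separately, while the glossary definition is wider. This concerns recording only and changes no dosing rule.

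**Data already collected.** Query Dosage Administration Record entries that give a laboratory-toxicity reason and have no matching AE. Split the existing table of dose reductions by reason by laboratory parameter and arm. If the database is locked, Protocol 9.3 allows changes only by joint written agreement; a listing of the unmatched entries with the split table would then serve.

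**Cost.** One clause in the protocol and the CRF instructions, a round of queries, one extended table, and more AE entries to code and assess.

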### **Unusually severe rejection episodes**

Allograft rejection is an expected event in all forms of transplantation and will not be considered an SAE even though it may require prolonged hospitalization and medical therapy. These events will be reported in the Rejection CRF and no SAE form has to be completed. However, if in the opinion of an investigator a rejection episode is unusually severe and warrants specific notification, then an SAE form must be completed and submitted according to SAE reporting procedures outlined in Section 8.1. In this particular case, information needs also to be reported in the Adverse Event CRF.

### **Infections**

All infection episodes must be recorded on the Infection CRF; they should not be collected on the AE CRF. Infections should be listed with severity, relationship, sample site, genus and species of microorganism specified, start and end dates, action taken.

**CMV infection:** Information will be captured on laboratory-defined CMV (antigenemia-positive, PCR positive), CMV syndrome (fever for the last 2 days, neutropenia, leukopenia, viral syndrome) and CMV-disease (organ involvement), on the CMV-specific CRF. CMV and HCV viral load (HCV positive patients only) will be measured locally at baseline, month 1, 3, 6, 12, for evaluation of incidence and severity. Suspected CMV infections will be recorded on the Infection CRF and on the CMV-specific CRF-field during visits. CMV infections will be also assessed by donor/recipient constellation (D+R+ / D-R- / D+R- / D-R+).

**HCV infection:** HCV information will be recorded on the Infection CRF. HCV viral load (HCV positive patients only) will be measured locally at baseline, month 1, 3, 6, 12, for evaluation of incidence and severity. HCV genotype will be assessed locally at baseline (HCV positive patients only).

### **7.6.2 Physical examination**

Information about the physical examination must be present in the source documentation at the study site.

Any clinically significant conditions that are present prior to the start of study drug intake must be recorded on the Relevant Medical History/Current Medical Conditions pages of the CRF.

All new conditions found after start of the study drug intake which meet the definition of an Adverse Event must be recorded on the Adverse Event part in the CRF.

### **7.6.3 Vital signs**

Height will be recorded at Screening visit (Visit 1) only. Vital signs will be recorded at every study visit, and include radial pulse rate, systolic and diastolic blood pressure and weight (kg). Blood pressure and pulse rate will be assessed after the patient has rested in the sitting position for at least five minutes; blood pressure should be assessed at the same arm each time of determination.

### **7.6.4 Laboratory evaluations**

The center's local laboratory will be used to analyze the clinical laboratory data during the study.

The following variables will be examined:

Hematology: hemoglobin, leukocytes (including differential blood count and absolute neutrophil count), platelet count, hematokrit (HK)

Blood chemistry: creatinine, urea/BUN, sodium, potassium, calcium, ALAT, ASAT, protein, AP, albumin, CRP, phosphate, magnesium, CPK, total bilirubin, glucose (fasting), cystatin C, Hb1c, LDH

Lipid profile: total cholesterol, HDL, LDL, triglycerides

Viral serology: Hepatitis B (HBsAg, only at Screening), HCV, CMV (including pp65 Ag)

Urinalysis: creatinine, protein, albumin

